5. REGISTRATION PROCEDURES

Organizational and Staff Recruitment

Organizational Surveys: The Executive Sponsor (or their designee) will complete the organizational surveys and may be asked to complete a short qualitative phone interview.

Staff Survey: The staff surveys will be completed by staff that are a part of the Change Team.

Physician Survey: The Physician Survey will be completed by physicians/prescribers working at the sites.

The Executive Sponsor will not have access to the survey data nor will they receive any data feedback or summaries from the surveys. The IRB approved consent form will describe that completing the staff or organizational survey infers their consent. For those who do not complete the survey, the survey will not be recorded and no record of the person not wanting to participate will be made. The consent form will be the first portion of the on-line survey to be administered through REDCap.

All surveys will be accessed through REDCap, a secure web-based platform, licensed by University of Wisconsin, that is used for building and managing online databases and surveys.

6. STUDY & TREATMENT PLAN

Study Design

The proposed study will implement a cluster randomized block design where staff are nested within sites. The community-based provider sites and jails will be grouped into homogeneous blocks and then randomly assigned into 2x2 design for each block. The forty-eights sites will be assigned to one of four study arms using a matching strategy within the blocks that groups four jail-clinic combination together prior to randomization. Each jail and CB treatment provider (or clinic) in these combinations will be treated as a site. For instance, if a jail has two post incarceration CB treatment providers (or clinics) in the trial, this will be 3 total sites (of the 48 sites). Within the matching block of 4 jail-clinic combinations, one jail-clinic combination will be randomized to an arm of the study. Twelve sites (that will consist of jails or post incarceration

CB treatment sites) will be assigned to each arm. The number of jails and post-incarceration sites per arm are expected to be balanced, with an anticipated 4 jails and 8 post-incarceration CB provider sites per arm.

Matching will be based on; a) number of clinic sites the jail will be including in the study (as part of the jail-clinic combination), population of the county where the jail is located, and whether or not the jail is currently providing MOUD to CJ population, and if so, what type of MOUD. The blocking procedure will reduce variability within treatment conditions and yield more precise estimates of treatment effects. This strategy will allow for the study team to examine the effects of High versus Low-Dose coaching and ECHO on MOUD use rates in large and small settings. In the study design, there will be a 12-month implementation period followed by 12 months to track sustainability. Data will be collected at baseline, 12 months and 24 months.

[figure not shown]
Intervention

There will be two “scaling-up practices” used in this study; NIATx Coaching and ECHO Clinical Mentoring. The study will look at combination of these two practices to create four intervention study arms;

- 1) High-Dose Coaching/ECHO,
- 2) Low-Dose Coaching/ECHO,
- 3) High-Dose Coaching/No ECHO, and
- 4) Low-Dose Coaching/No ECHO

Scaling up Practice #1: NIATx Coaching. NIATx framework provides each participating site with a NIATx Coach who is an expert in MOUD implementation and organizational change and will help the organization adopt, implement, and increase the use of MOUD. Coaches help the sites think through key issues, offer process improvement training, and suggest changes. NIATx coaches in the High-Dose and Low-Dose arms will interact with the organization described in Figure 1. The High-Dose coaches will conduct an on-site visit with the site Change Team and complete 11 monthly one-hour calls (months 2-12 of intervention) following the kick-off meeting. Coaches in the Low-Dose arm will hold a one-hour introduction call with the Site Change Team and conduct a two-hour NIATx training via webinar and three quarterly, one-hour calls at months 4, 8 and 12 with the Change Team following the kick-off meeting.

Figure 1: NIATx Coaching (During 12-month Intervention Period)

Step 1. Define Aims: Executive sponsor briefing on project during an in-person Kick-off meeting with Study Team & other Executive Sponsors.

Step 2. MOUD Baseline Assessment: Baseline will include buprenorphine, naltrexone & methadone capacity and Organizational Readiness Baseline Assessment. Assessment and reporting will be completed by Executive Sponsor or an administrator.

Step 3. Train Change Leader & Change Team: One Change Leader and up to 7 members identified by the organization (Change Team) will be trained to implement MOUD during the site visit or introductory call with the site change team.

Step 4. Monitor Progress: Track the number of buprenorphine, naltrexone & methadone capacity and use.

Step 5. Pilot Test Changes to implement MOUD using Plan Do Study Act (PDSA) approach.

Step 6. Sustain Successful Changes: Implement a plan to institutionalize gains to not revert to old ways. Leadership and medical team will be trained to sustain changes made.

Scaling up Practice #2: ECHO. The ECHO model connects MOUD prescribers and experts with primary care providers and medical teams to promote high-quality MOUD practices. ECHO is provided monthly through videoconferences. Experienced MOUD prescribers address topics such as counseling strategies, urine test interpretation, and transitioning from buprenorphine, naltrexone and methadone. Prescribers assigned to the two study arms that include ECHO will participate in 12, one-hour monthly ECHO Videoconferences.

Ten to eleven prescribers from the two study arms will be asked to volunteer to submit case studies. Prescribers who volunteer will receive instructions on how to write the case study and will receive a \$50 gift card as an incentive. One case study will be reviewed during each ECHO videoconference call in addition to a subject presentation.

Kick-Off Meeting

Prior to the start of the intervention(s), the Executive Sponsor and/or Change Leader (may also include Change Team members), as well as other key stakeholders, will be invited to attend a half-day in-person Kick-Off Meeting. The following material will be discussed; 1) Overview of Study and AIMs, 2) Current practices at sites, 3) Best Practice Examples, 4) Ways to Expand Capacity, and 5) NIATx Process.

We anticipated holding up to and no more than eight kick-off meetings. Meeting locations will be determined based on grouping participating sites that are in close proximity to each other to keep travel minimal.

Table 1: Outline of the Four Study Arms & Site Responsibilities:

ARM	NIATx Coach	ECHO
High-Dose Coaching & ECHO	
 • Key stakeholders attend an in-person Kick-Off Meeting with Study Team & Coaches • 4-hour onsite visit 
 ◦ 1-hour meeting w/Executive Sponsor & tour facility ◦ NIATx training with Change Leader/Team • 11 monthly (one-hour) coaching calls 	
 • Prescribers participate in 12 monthly (one-hour) video conference calls
Low-Dose Coaching & ECHO	
 • Key stakeholders attend an in-person Kick-Off Meeting with Study Team & Coaches • One-hour conference call with Executive Sponsor • Two-hour NIATx webinar training with Change Leader/Team • Three (one-hour) coaching calls at months 4, 8, and 12 with Change Leader/Team 	
 • Prescribers participate in 12 monthly (one-hour) video conference calls
High-Dose Coaching / No ECHO	
 • Key stakeholders attend an in-person Kick-Off Meeting with Study Team & Coaches • 4-hour onsite visit 
 ◦ 1-hour meeting w/Executive Sponsor & tour facility ◦ NIATx training with Change Leader/Team • 11 monthly (one-hour) coaching calls 	
Low-Dose Coaching / No ECHO	
 • Key stakeholders attend an in-person Kick-Off Meeting with Study Team & Coaches • One-hour conference call with Executive Sponsor • Two-hour NIATx webinar training with Change Leader/Team • Three (one-hour) coaching calls at months 4, 8, and 12 with Change Leader/Team 	

Data Source

Table 2 shows a complete list of Measures, Sources, and Tool/Frequency. The Executive Sponsor, Change Leader and Change Team at each jail and community-based provider site will be asked to complete one or two of the three main surveys based on their role(s) within the study: Organizational Survey, Staff Survey, and Physician Survey. Site staff participants will be sent links to complete the survey(s) via REDCap. Each organizational site will receive a \$1000 stipend per year for two years once all organizational, physician, and staff surveys have been completed.

The trial has 4 study arms that will have staggered starts in order to have sufficient training resources for the trial. Each arm will have 12 organizations/sites with N=48 total.

Organizational Surveys & Data:

Organizational surveys will be completed by Executive Sponsor (or their designee) three times during the project (baseline, 12 months and 24 months). The baseline survey will be conducted by phone interview with all 48 sites. To increase survey completion rates for the organizational surveys, the research team at UW will conduct follow-up phone calls and e-mails with the Change Leaders at Week 1 of post-survey distribution to assure the survey receipt, then at Weeks 4 and 12-post survey distribution if surveys are not complete.

We will assess Organizational Traits, Client Traits, Staff Characteristics, and number of prescribers at the sites at three points during the study - at organizational baseline (baseline), at end of the intervention period (month 12) and at end of sustainability period (24 months) using a mix of organizational and administrative data.

Each survey will take approximately 45 minutes to complete. This will result in 48 unique staff participants at baseline, and 4 new people per round at post-intervention (m12) and post-sustainability (m24), assuming 10% turnover at each round. This will result in a total of 56 unique participants and 144 total surveys.

Staff Surveys & Data:

The designated Executive Sponsor or the Change Leader at each site will manage staff member recruitment to construct a change team of up to a seven (7) member Change Team. Up to two of the team members will be physicians. Each member of the change team as well as the change leader will be asked to complete staff surveys at baseline, 12m, and 24ms for a total of 8 "staff" surveys per site. Information on the implementation process will be gathered from site staff members during surveys and interviews.

The full Staff Survey including Organizational Readiness for Implementing Change (ORIC), Organizational Climate-Stress, Attitudes toward MOUD and Program Sustainability, will be administered three times during the study (baseline, 12m, 24m). Each survey is expected to take approximately 20 minutes or less to complete. Staff completing the surveys will receive consent documents when they are sent the survey link via REDCap. To increase survey

completion rates for the Staff Surveys, the research team at UW will conduct follow-up phone calls and e-mails with the Change Leaders at Week 1 of post-survey distribution to assure the survey receipt, then at Weeks 4 and 12-post survey distribution if surveys are not complete. Each survey cycle, at months listed above, will include up to 384 people per cycle. The 384 staff will include up to 8 participants from the 48 sites and will include the Change Leader (supervisor/member of the leadership staff), and up to 7 team members part of the Change Team (CJ staff, prescribers, clinicians, nurses, counselors, social workers, etc). Since many of the same staff will likely complete surveys in successive cycles, 536 unique staff are expected for survey completion across all three cycles. The 536 unique people projected assumes 20% or 76 new people per round occurs post-intervention and post sustainability round. There will be a total of 1,152 surveys.

Physician Surveys & Data:

Collecting physician attitudes toward MOUD will occur at months 0, 12, and 24. An average of two prescribers are anticipated per site. Each survey will take 15 minutes or less to complete. Staff completing the surveys will receive consent documents when they are sent the survey link via REDCap. To increase survey completion rates for the Physician Surveys, the research team at UW will conduct follow-up phone calls and e-mails with the physicians at Week 1 of post-survey distribution to assure the survey receipt, then at Weeks 4 and 12-post survey distribution if surveys are not complete. This will result in 96 unique prescriber participants at baseline, and 9 new people per round at post-intervention (m12) and post-sustainability (m24), assuming 10% turnover at each round. This will result in a total of 114 unique prescribers and 288 surveys (@ 96/cycle).

The grand total of organizational surveys, at n=144, staff surveys at n=1,152, physician surveys at n=288. TOTAL will be N=1,584.

Administrative & Site Aggregate Data:

Administrative Jail Data will be collected from all 24 jail sites once every year for two years. We anticipate the data will include de-identified screening, assessment and/or intake data, demographic information, date entered/exited jail, sentence and length, etc.

Administrative State Criminal Justice Data will be obtained from state databases for all states that have a jail/community-based provider participating in the study. De-identified data will be provided once every year for two years for the participating jail jurisdictions (e.g. in Wisconsin it is counties). Data may include arrest dates, arrest offenses, court outcomes, sentence and length, etc.

Health and Treatment Provider Data will be provided by all 24 community-based treatment providers once every year for two years. De-identified data for jail based referrals would include number of referrals to OUD care, number of referrals to behavioral therapy or counseling, dates/type of care, MOUD units received, Medicaid payment data, etc.

Monthly Tracking Data will be provided by all 48 jails/community-based treatment providers on a monthly basis via spreadsheet provided by study team. Captured data for the jails will include MOUD treatment data, number screened for OUD, number receiving MOUD, number of

individuals who received naltrexone, buprenorphine and methadone and number of injections/slots. Captured data for the community-based treatment providers will include number referred from the jail for OUD, number receiving MOUD, number of individuals who received naltrexone, buprenorphine and methadone and number of injections/slots.

All suggested data requirements are included in the Information Sheet provided to each site prior to participation in the study.

Table 2: Measures, Sources, and Tool/Frequency

Measurement	Measure Source	Data Source/Frequency
Descriptive Statistics		

Organizational traits (survey source): Admissions (state), Rural v. Urban (state), organizational readiness (staff), MOUD type (org), funding (org), # of practitioners (org)
 
Client traits: Age, gender, ethnicity, highest education level, employment indicator, place of residence, type of offense, Medications/Treatment offered (date(s) receiving MOUD), mental health comorbidity, OUD history, Disciplinary actions/incident reports, types of offenses
 
Staff Characteristics: Age, Gender, Ethnicity, Certification or education level, years of training, tenure on the job
	Organization & Administrative Data	
 Organizational Survey 
 Baseline, 12m, 24m State CJ Database & Jail Administrative Database 
 Baseline, 12m, 24m Monthly Tracking Site Spreadsheet Organizational Survey 
 Baseline, 12m, 24m
Reach		
% of patients initiated/begin MOUD; Days engaged in MOUD	Organization	
 Monthly Tracking Site Spreadsheet 
 Completed by Jail/Clinic Manager/Data Liaison Or State Databases
Effectiveness		
Re-Arrest Data: Arrest dates, Arrest Offense (charge), Felony/Misdemeanor indication, Outcome (convicted, not convicted, sentence, start and end date of sentence),	State Database	
 State CJ databases 
 Baseline, 12m, 24m

Adoption		
% of prescribers using MOUD	Organization	
 • Organizational Survey 
 ○ Baseline, 12m, 24m
Staff Attitudes Toward MAT	Knudsen, Ducharme, Roman & Link ⁴²	
 • Staff Survey 
 ○ Baseline, 12m, 24m
Physician Satisfaction with MOUD	Modified Physician Worklife Survey	
 • Physician Survey 
 ○ Baseline, 12m, 24m
Implementation		
Organizational Readiness for MOUD	ORIC ³⁹	
 • Organizational Survey 
 ○ Baseline, 12m, 24m
Organizational Climate: Stress	TCU SOF ⁴¹	
 • Staff Survey 
 ○ Baseline, 12m, 24m
Maintenance		
Likelihood of MOUD sustainability	Program Sustainability Assessment Tool ⁴⁰	
 • Staff Survey 
 ○ Baseline, 12m, 24m
NIATx Fidelity & ECHO Fidelity	Organization (using a scale designed for this study)	
 • Organizational Survey 
 ○ Baseline, 12m, 24m

Qualitative Interviews

Qualitative data will be gathered from organizational staff at two points; pre-intervention (baseline) and post-intervention (12 months).

Baseline qualitative phone interviews will be completed with leadership staff at 24 randomly selected sites, six sites within each study arm. Interviews will last approximately 30-45 minutes in length and will be conducted with up to two people at each site. The interviews will be audio-taped (with staff participant permission), but the staff person's identity will be protected and in no way be linked to the results. Interviews will be semi-structured and gather information that is not included within the organizational surveys that will be completed throughout the study. This includes information about site structure and process, culture surrounding justice-involved clients, motivation for serving OUD population and approaches to organizational change. Examples of open-ended questions that will be asked;

1. Please walk me through how a justice-involved client comes to your service?
2. Are your justice-involved clients integrated into your general clientele?
3. Please tell me about the last time your organization made a change to its processes?

Post-intervention qualitative phone interviews at 12 months will be conducted with the Change Leader at 24 selected sites. Interviews will last approximately 20-30 minutes and will be audio-taped (with staff participant permission), but the staff person's identity will be protected and in no way be linked to results. Sites will be chosen by taking the three highest achieving sites and the lowest achieving sites in each of the four arms, providing for 24 interviews. Sites will be ranked based on the percentage of eligible individuals who received MOUD within the 12-month intervention period. During the interview, Change Leaders will be asked to review their site outcome data and provide their experience and feedback about the implemented intervention(s).

Example of open-ended questions included;

1. What do you see when you look at this data from your site?
2. What helped you to achieve these results?
3. What barriers got in the way?

We will use University of Wisconsin Box to store data received from all sites.

Unanticipated events

Should any unanticipated problems arise, they will be reported to WIRB per the appropriate IRB's guidance on unanticipated problems and reportable events.

Privacy and Confidentiality

Since community-based organizations and jail sites will play a role in the testing of the NIATx and ECHO interventions, we view staff members as human subjects. For the project's evaluation plan, we will address human subjects' protection for staff. Clients are not being addressed since they are not the focus of the intervention, while the organization's leadership, staff and prescribers are. The data to be collected in the evaluation will come from existing de-identified client data collected in state administrative databases as well as organizational and staff surveys, and staff interviews. Table 3 (below) briefly describes the individuals referred to in the protection plan who will have access to the project data and their level of access.

Table 3: Research Participant Overview

Title	Affiliation	Access
Scientific Directors (PI)	UW-Madison & George Mason University	Limited Data Set client administrative data, survey, and interview data
Project Team (researchers/students)	UW-Madison & George Mason University	Limited Data Set client administrative data, survey, and interview data
State database administrators	States with participating sites	They will not receive or view any administrative, survey, or interview data
Executive Sponsor (Site staff member in administration, executive or management role)	Participating sites	They will not receive or view any administrative, survey, or interview data
Change Team Leader (Site staff member in a management role)	Participating sites	They will not receive or view any administrative, survey, or interview data
Change Team (Site staff members-Prescribers (at least one), clinicians, nurses, counselors, social workers, etc)	Participating sites	They will not receive or view any administrative, survey, or interview data

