3. STUDY OBJECTIVES

The specific aim of this study is to compare High-Dose NIATx Coaching/ECHO, Low-Dose NIATx Coaching/ECHO, High-Dose NIATx Coaching/No ECHO, and Low-Dose NIATx Coaching/No ECHO. Impact will be measured using the RE-AIM framework:

- *Reach* (primary aim) measured as the percent of eligible justice involved patients who 1) are initiated onto any MOUD (buprenorphine, extended-release injectable naltrexone, or methadone), and 2) engaged with MOUD use.
- *Effectiveness* measured in terms of impact of MOUD involvement on re-arrest rates.
- *Adoption* measured as the percent of eligible clinicians in jail and/or community providers who use MOUD.
- *Implementation* measured by an organizational readiness for MOUD implementation over time and intervention fidelity scale (*for NIATx and ECHO*).
- *Maintenance* measured as the likelihood of organizations sustaining provision of MOUD utilization (organizational sustainability scores at 12 and 24 months of intervention) and we will continue to collect Reach, Effectiveness, and Implementation measures during the maintenance phase (Ms 12-24).

Study Coordination

The UW-Madison Center for Health Enhancement Systems Studies (CHESS) and George Mason University Center for Advancing Correctional Excellence! are the coordinating sites for this study. George Mason holds the grant award for the larger study this research is embedded in. The UW site will oversee all recruitment and study implementation activities which includes:

- developing organizational site-specific recruitment and data collection processes that meet study objectives;
- training staff on protocol procedures prior to start of recruitment and continuous monitoring to assure compliance with the protocol and human subjects regulation;

- communicating with clinic site staff as needed via conference calls to monitor progress, inform of protocol changes/distribute new version of protocol, and address unanticipated issues or challenges;
- manage all study data;
- oversee analysis; and
- oversee publications and presentations.

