We will test the mediation effect of each potential mediator at each time point as well as across time. The R package 'mediation,' will estimate the causal mediation effects, examine moderated mediation effects, and conduct sensitivity analysis.⁷⁰

Effectiveness analysis:

We will compare MOUD use and retention rates in the 4 different arms using hierarchical linear models, where arm membership is used as the treatment assignment. We will examine the distribution of this outcome measure and will implement an appropriate transformation or nonlinear link function when appropriate (e.g., logistic, Poisson, exponential). Monthly data collection of the Effectiveness as well as Reach (MOUD use) measures, allows for analysis after each stage of NIATx and ECHO.

Table 4: Initiation & Retention

	Data	Source
Initiation	
• # of clients initiated on MOUD• # on MOUD	Organizational Spread Sheet
Retention	
• # of injections• # of weeks on Buprenorphine (30-Day Discontinuation)• # of methadone doses	State Database

Qualitative Analysis:

The qualitative analysis will be conducted by project staff, supervised by the qualitative methodologist, who will ensure that proper and consistent interviewing and analysis techniques are used. Project staff will conduct the interviews, which will be audio recorded and transcribed verbatim. Interviews with leadership personnel will focus on organizational culture, including the organization's approach to making process changes, as well as motivations and expectations for working with justice-involved populations. Interviews with staff will focus on the staff's perspectives on their organizations' experiences with identifying and implementing process changes. Project staff will conduct a directed content analysis of these data. Qualitative data will be summarized and analyzed to detect patterns in individual and clinical approaches to change that have been successful. This description will enhance our understanding of how the NIATx and ECHO models work in criminal justice settings and criminally involved populations, promoting valuable insights that can be applied to future dissemination and implementation of evidence-based practices.

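### No rule says how a person started on MOUD in jail and continued at the partner clinic counts toward Reach, so clinic Reach can move with jail practice alone, in either direction

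*Combined protocol and SAP*

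**What the plan says.** **Definition.** Section 3 makes Reach the primary aim, "measured as the percent of eligible justice involved patients who 1) are initiated onto any MOUD", with a second component, "2) engaged with MOUD use". Table 2 gives the measure as the percentage "of patients initiated/begin MOUD; Days engaged in MOUD", taken from the monthly site spreadsheet or from state databases.

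**Monthly fields (section 6, Administrative & Site Aggregate Data).** For jails: "Captured data for the jails will include MOUD treatment data, number screened for OUD, number receiving MOUD". For clinics: "Captured data for the community-based treatment providers will include number referred from the jail for OUD, number receiving MOUD".

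**Units.** Section 6, Study Design: "Each jail and CB treatment provider (or clinic) in these combinations will be treated as a site". The same section randomizes whole jail-clinic combinations within blocks of four. Section 9 instead matches single clinics in fours and randomizes one to each arm.

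**Analysis.** Table 4 in section 10 files two counts under Initiation, both from the organizational spreadsheet: the number "of clients initiated on MOUD" and the number on MOUD. The model text in section 10 takes the percentage using MOUD as the outcome, with a random effect for program. The site ranking for the 12-month interviews (section 6) uses the percentage who received MOUD.

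**Not stated anywhere:** which count is the Reach numerator, what the eligible denominator is at each type of site, how a person already on MOUD at referral is classed, and whether a person seen at both sites is counted once.

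**The concern.** The clinic's pool is fed by the jail. Under the listed fields, someone started in jail, referred and continued is in the jail's screened and receiving counts and again in the clinic's referred and receiving counts. What the clinic sheet shows then depends partly on how many people arrive already treated, which the clinic does not control.

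Clinics are at least half of the sites on any version of the plan: 24 of 48 (section 6, administrative data), 32 of 48 (section 6, Study Design, and section 10) or 36 of 48 (section 9). In the layout of section 10, 16 jails and 32 clinics, there are on average two clinics per jail, so one change in jail practice can appear in three program-level outcomes. If the results are read as evidence about clinics, a jail effect is credited to them. In the pooled model the same effect carries the wrong weight, and sites in one combination are correlated in a way that a program-only random effect does not capture.

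**Working it through.** **1. The plan's own figures.** The plan gives no expected Reach values, so there is none to reproduce. Its one checkable figure is power of at least .85 for coaching (42 programs, 75 patients each, d = 0.51, ICC 0.10, alpha 0.05, taken as two-sided). The noncentrality is sqrt(J·d² / (4·(ICC + (1−ICC)/n))) = sqrt(42 × 0.2601 / (4 × 0.112)) = 4.94. With 40 df this gives power 0.998, so the stated bound is met. If 10% to 50% of the records at an assumed 28 retained clinics are duplicates, unique patients fall from 3,150 to between 2,940 and 2,100, and power stays at about 0.997 to 0.998. The problem is therefore one of meaning, not of nominal power.

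**2. Clinic Reach on each possible numerator.** The documents give none of the following inputs, so all are assumptions:
- s = share of referrals started in the jail, moving from 20% to 40%
- h = share of those continued at the clinic, 50% to 100%
- c = s × h = share of referrals carried over on MOUD
- p = clinic start rate among all other referrals, 10% to 50%, held fixed so that clinic practice does not change
- the clinic's receiving count is taken to cover jail referrals

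The three measures are:
- receiving / referred = c + (1−c)p, which changes by Δc·(1−p)
- initiated / all referred = (1−c)p, which changes by −Δc·p
- new starts / referrals not already on MOUD = p, which does not change

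| h | p | c | receiving / referred | initiated / all referred |
|---|---|---|---|---|
| 100% | 10% | 0.20 → 0.40 | 28% → 46% (+18) | 8% → 6% (−2) |
| 100% | 30% | 0.20 → 0.40 | 44% → 58% (+14) | 24% → 18% (−6) |
| 100% | 50% | 0.20 → 0.40 | 60% → 70% (+10) | 40% → 30% (−10) |
| 50% | 10% | 0.10 → 0.20 | 19% → 28% (+9) | 9% → 8% (−1) |
| 50% | 30% | 0.10 → 0.20 | 37% → 44% (+7) | 27% → 24% (−3) |
| 50% | 50% | 0.10 → 0.20 | 55% → 60% (+5) | 45% → 40% (−5) |

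Receiving over referred rises by 5 to 18 points. Initiated over all referred falls by 1 to 10 points, because already-treated referrals stay in the denominator.

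**3. Limiting case.** If the clinic starts nobody, receiving / referred equals the carried-over share (20% at c = 0.20, 40% at c = 0.40), while initiated / referred is 0% throughout.

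**4. Dependence.** Treat the combination as the cluster, assuming three sites and 225 patients each and that the ICC of 0.10 applies at that level. The noncentrality for 16 combinations is sqrt(16 × 0.2601 / (4 × 0.104)) = 3.16, giving power 0.84 with 14 df. For 14 combinations it is 2.96, giving 0.78 with 12 df. On these assumptions, the level that the model omits costs more power than duplicated records do.

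**The case against.** **Reach is defined on initiation.** Sections 3 and 10 (Table 4) both name initiation, and Table 4 has a separate initiated count. A reader might infer from the monthly fields that clinic Reach necessarily rises with jail starts. The documents do not establish that: on the initiated count it falls. But Table 4 lists both counts without choosing, does not define initiated for a hand-over, and sits beside model and ranking text that refers to using and receiving. The undefined numerator stands as the finding.

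**Continuation is part of Reach.** A handed-over patient properly contributes to the engagement component at the clinic. That is right. The objection is only to counting the same person as an initiation there.

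**The field list may be incomplete.** Section 6 says what the captured data will include and points to an Information Sheet that is not among the documents. Provider and client data also carry dates of care. These might identify carry-overs, but the yearly jail and provider data are de-identified and no key linking jail to clinic is described, so later repair cannot be assumed.

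**No arm difference from nothing.** A reader might infer that carry-over can create a coaching or ECHO effect where none exists. Under section 6 a jail and its clinics share an arm, so with no arm effect on jail starts, carry-over produces no expected difference between arms. The plan also specifies no clinic-only contrast. What remains is attribution, weighting and dependence. Under the single-clinic randomization of section 9, one arm's jail starts could enter a clinic in another arm, so the two sections must be reconciled.

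**Larger sizes.** With 300 screened, all jail-started people and 30% of the rest referred, full continuation and a clinic start rate of 10%, tripling the jail rate from 10% to 30% moves receiving over referred from 38.1/111 = 34% to 96.3/153 = 63%. On initiated over all referred it moves from 8.1/111 = 7.3% to 6.3/153 = 4.1%. At the higher rate, recipients summed across the two sheets are 186.3 for 96.3 people, or 1.9-fold. The arithmetic is correct, but the inputs are extreme, and no section proposes adding recipients across sites.

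**Conclusion.** The concern holds as a gap in the definition of the primary outcome. A person started in jail and continued at the clinic falls in both sites' listed counts, and no rule settles how that person enters Reach. With clinic practice unchanged, a rise in the jail-started share of referrals from 20% to 40% moves clinic Reach by +5 to +18 points on one permitted reading and −1 to −10 points on the other. These sizes rest on assumed clinic start rates of 10–50% and continuation of 50–100%; the direction on each reading does not.

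Under the randomization in section 6, a jail effect is misattributed to clinics. It gets extra weight on the receiving count, or is partly offset on the initiated count. Sites within a combination also become dependent beyond what the program-only random effect allows. The documents do not support saying that double counting in Reach is planned, or that it would by itself produce an intervention effect.

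**What to change.** 1. Add two counts to the clinic's monthly sheet: already on MOUD when referred, and first MOUD start at this clinic.
2. In Table 4, define initiation as new starts at that site and name it as the initiation numerator. Count hand-overs under engagement only.
3. Report Reach per jail-clinic combination as (jail new starts + clinic new starts) / people identified with OUD in the jail. This matches the unit randomized in section 6. In the 300-person illustration, if all 300 were identified with OUD, it gives 38.1/300 = 12.7% and 96.3/300 = 32.1%, with each start entered once. The jail sheet must then record new starts and the number identified, where these differ from the numbers receiving and screened.
4. Add a combination-level random effect, and reconcile the randomization units and clinic numbers in sections 6, 9 and 10.
5. Show clinic new starts over referrals not already on MOUD only as a secondary, descriptive measure. It does not move with jail starts when the clinic start rate is fixed, but the intervention can change who is left in that denominator, so arms may not be comparable on it.

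The cost is slightly more site reporting and some analysis-plan wording. The combination-level term may also lower the power that can be claimed (0.84 or 0.78 under the assumptions above). Person-level de-duplication over 12 months should not be required, because the monthly data are site counts and no linkage key is described. A person who stops and later restarts at the other site may therefore still be recorded twice, and the report should say so.
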